- Number of days from randomization to the first day on which the subject satisfies one of the following three categories from the ordinal NIAID 8- point Clinical Progression Outcomes scale collected daily from randomization through Day 28:
 - Hospitalized, not requiring supplemental oxygen - no longer requires ongoing medical care;
 - Not hospitalized, limitation on activities and/or requiring home oxygen;
 - *Not hospitalized, no limitations on activities.*

To compare changes in clinical status of patients enrolled to CX-4945 treatment arm as compared to the control arm at Day 14 and Day 28.

- Difference in percentage of subjects with clinical recovery compared at Day 14 and Day 28. Clinical recovery is defined as:
 - Discharge from the hospital, or alleviation of cough (defined as mild or absent in a patient reported scale of 0=absent, 1=mild, 2=moderate, and 3=severe). Improvement must be sustained for at least 48 hours.
 - normalization of fever (defined as $<36.6^{\circ}$ C from axillary site, or $<37.2^{\circ}$ C from oral site or $<37.8^{\circ}$ C from rectal or tympanic site), normalization of respiratory rate (<24 bpm while breathing room air), resolution of hypoxia (defined as SpO2 \ge 93% in room air or P/F \ge 300

CONFIDENTIAL Page 10 of 66

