3. OBJECTIVES AND ENDPOINTS

Primary Objective	Primary Endpoint
To assess safety and tolerability of CX-4945 administered orally twice daily to patients with severe COVID-19	• Adverse Events experienced by patients from randomization to Day 60 (including vital signs, physical findings, clinical laboratory, and ECG results) as characterized by type, frequency, severity (as graded by Common Terminology Criteria for Adverse Events (CTCAE version 5.0), timing, seriousness, and relationship to study therapy.
Secondary Objectives	Secondary Endpoints
• To compare time to clinical recovery in the CX-4945 treatment group evaluated from randomization through Day 28 as compared to the control arm.	• Number of days from randomization to discharge, or alleviation of cough (defined as mild or absent in a patient reported scale of 0=absent, 1=mild, 2=moderate, and 3=severe). Improvement must be sustained for at least 48 hours.
	• Number of days from randomization to normalization of fever (defined as <36.6°C from axillary site, or < 37.2°C from oral site or < 37.8°C from rectal or tympanic site), normalization of respiratory rate (< 24 bpm while breathing room air), resolution of hypoxia (defined as SpO2 ≥ 93% in room air or P/F ≥ 300 mmHg). All these improvements must be sustained for at least 48 hours.
	 Number of days from randomization to the first day on which the subject satisfies one of the following three categories from the ordinal NIAID 8-point Clinical Progression Outcomes scale collected daily from randomization through Day 28:
	Hospitalized, not requiring supplemental oxygen - no longer requires ongoing medical care;
	 Not hospitalized, limitation on activities and/or requiring home oxygen;
	Not hospitalized, no limitations on activities.
To compare changes in clinical status of patients enrolled to CX-4945 treatment arm as	Difference in percentage of subjects with clinical recovery compared at Day 14 and Day 28. Clinical recovery is defined as:

CONFIDENTIAL Page 22 of 66

s. ty	ite, or < 37.2°C from oral site or < 37.8°C from rectal or ympanic site), normalization of respiratory rate (< 24 bpm
a	while breathing room air), resolution of hypoxia (defined as $SpO2 \ge 93\%$ in room air or $P/F \ge 300$ mmHg). All these mprovements must be sustained for at least 48 hours.
Day	centage of participants at each clinical status at Day 14 and 28 assessed by using the ordinal NIAID 8- point Clinical gression Outcomes scale:
1) L	Death;

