	Hospitalized, on invasive mechanical ventilation or acorporeal membrane oxygenation (ECMO);
· · · · · · · · · · · · · · · · · · ·	Hospitalized, on non-invasive ventilation or high flow gen devices;
4) H	Hospitalized, requiring supplemental oxygen;
	Hospitalized, not requiring supplemental oxygen - requiring oing medical care (COVID-19 related or otherwise);
· ·	Hospitalized, not requiring supplemental oxygen - no longer uires ongoing medical care;
	Not hospitalized, limitation on activities and/or requiring ne oxygen;
8) N	ot hospitalized, no limitations on activities
evidence of anti-viral activity of CX-4945 as compared to the Day	Gerence in proportions of patients with conversion of tive RT-PCR to negative RT-PCR as assessed at Day 1, 8, Day 14 and Day 28
	inges in chest imaging from Screening (Day 0)to Day 5 or 14 (if applicable) as defined by:
0]	Number of quadrants/ pulmonary lobes affected

CONFIDENTIAL Page 23 of 66

	 Change in number and/or size of COVID-19 pulmonary lesions (ground-glass opacity, consolidation, mix pattern) assessed by chest CT/X-ray
To evaluate the Clinical Benefit of Silmitasertib (CX-4945) relative to the control arm in patients with Severe COVID-19.	 Days of hospitalization from randomization through Day 28. Days of supplemental oxygen (if applicable) from randomization through Day 28. All-cause mortality status: the number of deaths occurred in each treatment group from randomization through Day 60. Days of non-invasive ventilation/high flow oxygen (if applicable) from randomization through Day 28. Days of invasive mechanical ventilation/ECMO (if applicable) from randomization through Day 28. Number of patients returned to room air after randomization through Day 14 or Day 28. Change in pulse oxygen saturation (SpO2) from randomization to Day 4, 8, 11, 14 and 28. Number of documented venous thromboembolism (VTE), arterial thrombosis (stroke, myocardial infarction, other) and microthrombosis events from randomization through Day 28. Changes in EQ-D5-5L (used as an indicator of symptom improvement) from randomization to Day 8, 14 and 28.
To evaluate changes in inflammatory markers	 Changes in plasma IL-6 level from randomization to Day 4, 8, 11, and 14 Changes in CRP, LDH, CPK, ferritin, D-dimer from randomization to Day 4, 8, 11, and 14

CONFIDENTIAL Page 24 of 66

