8.2.2.3. COVID-19 8-Point Clinical Progression Outcomes Scale

Progression is assessed on COVID-19 8-point ordinal scale collected daily from randomization through Day 28, regardless of discharge or treatment discontinuation status, to adequately capture relevant COVID19 outcomes. Remote data collection methods, such as electronic data collection, phone, and telehealth assessments can be used after patient discharge from the hospital through Day 28 (see **Section 1.3**). The ordinal scale of patient health status ranges from: 1) Death; 2) Hospitalized, on invasive mechanical ventilation or extracorporeal membrane oxygenation (ECMO); 3) Hospitalized, on non-invasive ventilation or high flow oxygen devices; 4) Hospitalized, requiring supplemental oxygen; 5) Hospitalized, not requiring supplemental oxygen - requiring ongoing medical care (COVID-19 related or otherwise); 6) Hospitalized, not requiring supplemental oxygen - no longer requires ongoing medical care; 7) Not hospitalized, limitation on activities and/or requiring home oxygen; 8) Not hospitalized, no limitations on activities.

8.2.2.4. Pulse Oxygen Saturation (SpO2):

Measuring the amount of oxygen-carrying hemoglobin in the blood relative to the amount of hemoglobin not carrying oxygen will be done at the time points described in the Schedule of Activities (see Section 1.3).

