9.3. SAMPLE SIZE DETERMINATION AND RATIONALE

A total of 40 subjects will be randomized 1:1 in this study. The sample size is based on clinical judgment. No statistical power calculation will be used to establish the sample size for this proof-of-concept study.

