9.8.4.1. Efficacy Analysis

Analysis of the efficacy endpoints will be summarized according to the variable type and will be detailed in the SAP:

CONFIDENTIAL Page 51 of 66

• Continuous data:

- o If the normality assumption is met, Analysis of Covariance (ANCOVA) would be used.
- If the normality assumption is not met, a non-parametric method or a rank –
 ANCOVA analysis i.e., an ANCOVA analysis on rank-transformed data will be used.
- Categorical data summaries will be based on logistic regression or proportional odds model will be used.
- Time-dependent data: Cox proportional hazards model will be used to analyze time dependent data and Kaplan-Meier methods will be used to depict the time to event data.

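### Time to recovery through Day 28 is analysed by Kaplan-Meier and Cox with no rule for patients who die unrecovered; if they are censored at death, recovery is overstated and an arm with excess deaths can look neutral on these endpoints

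*Combined protocol and SAP*

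**What the plan says.** The first secondary objective in Section 3 is "To compare time to clinical recovery in the CX-4945 treatment group evaluated from randomization through Day 28 as compared to the control arm". Three time-to-recovery endpoints serve it. One is based on discharge or relief of cough, and one on fever, respiratory rate and hypoxia. The third is the "Number of days from randomization to the first day on which the subject satisfies one of the following three categories" at the good end of the 8-point scale. None of the three definitions mentions death.

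The protocol does provide for deaths elsewhere. Section 8.2.2.3 puts death at the bottom of the scale that is collected daily to Day 28: "The ordinal scale of patient health status ranges from: 1) Death". Section 3 lists all-cause mortality separately, as "the number of deaths occurred in each treatment group from randomization through Day 60".

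On method, Section 9.8.4.1 says: "Cox proportional hazards model will be used to analyze time dependent data and Kaplan-Meier methods will be used" for display. It gives no censoring rule, does not name death as a competing event, and does not mention cumulative incidence. It also says "Analysis of the efficacy endpoints will be summarized according to the variable type and will be detailed in the SAP". Sections 9 and 9.8 describe that SAP as a separate document, to be approved before database lock; it is not part of the text under review. Section 9.7.3 applies multiple imputation to missing efficacy data and does not address values after death.

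**The concern.** A patient who dies without recovering can no longer recover, so death competes with recovery. If that patient is censored on the day of death, Kaplan-Meier treats the patient as someone who would have gone on to recover at the same rate as those still alive and in follow-up. The curve then no longer estimates the share of randomized patients who recover. It is too high in both arms, and the gap is larger in the arm with more deaths. The Cox ratio from the same data compares recovery rates among patients still alive and unrecovered, so extra deaths in one arm leave it largely unmoved.

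Section 2.3 says that the secondary objectives will supply the initial assessment of potential benefit, and time to recovery is listed first among them. The trial is open label (Section 9.5) and the SAP need only be approved before database lock. An unstated rule could therefore be settled after deaths by arm are known.

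**Working it through.** **Plan's own figure.** There is none to reproduce. Section 9.3 says "A total of 40 subjects will be randomized 1:1 in this study" and "No statistical power calculation will be used to establish the sample size". The documents give no recovery rate, death rate or effect size, so every rate below is an assumption.

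**Model.** Constant daily hazards over 28 days: recovery r, the same in both arms, and death d, which differs by arm.

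- True share recovered by Day 28: r/(r+d) × [1 − exp(−28(r+d))]
- Share dead unrecovered by Day 28: d/(r+d) × [1 − exp(−28(r+d))]
- One minus Kaplan-Meier with deaths censored at death: 1 − exp(−28r), which does not contain d

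**Main case: r = 0.05; d = 0.02 (Arm A) and 0.005 (Arm B).**

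- Arm A: 28 × 0.07 = 1.96 and 1 − exp(−1.96) = 0.859. Recovered: 0.05/0.07 × 0.859 = 61.4%. Dead: 0.02/0.07 × 0.859 = 24.5%.
- Arm B: 28 × 0.055 = 1.54 and 1 − exp(−1.54) = 0.786. Recovered: 0.05/0.055 × 0.786 = 71.4%. Dead: 0.005/0.055 × 0.786 = 7.1%.
- Kaplan-Meier: 1 − exp(−1.4) = 75.3% in both arms.

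The true difference is 10 percentage points and the display shows none. Kaplan-Meier overstates recovery by about 14 points in Arm A and 4 in Arm B. In simulated trials the Cox ratio is about 1.0 with deaths censored at death. It is about 0.8 (0.79 to 0.82 across runs and sample sizes) with deaths kept at risk as not recovered to Day 28.

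**Milder case: r = 0.06; d = 0.015 and 0.0075.** Mortality is 17.6% versus 9.4%. True recovery is 70.2% versus 75.5%, and Kaplan-Meier gives 81.4% in both arms. The ratio is 0.99 with deaths censored at death and 0.89 with deaths kept to Day 28.

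**Range over other assumptions.** Here control mortality is fixed at 10% and the recovery hazard is equal in the two arms.

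| Control recovery | Arm A mortality | True Arm A recovery | Kaplan-Meier, both arms |
|---|---|---|---|
| 60% | 20% | 55.4% | 64.4% |
| 60% | 30% | 50.7% | 64.4% |
| 70% | 20% | 64.2% | 75.5% |
| 70% | 30% | 58.2% | 75.5% |
| 80% | 20% | 72.6% | 87.1% |
| 80% | 30% | 65.0% | 87.1% |

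The loss of recovery that the display would not show is about 5 to 15 points (60 − 55.4 = 4.6 up to 80 − 65.0 = 15.0).

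**Equal deaths.** With 70% recovered and 10% dead in both arms, both Cox ratios are about 1.0, but Kaplan-Meier still reads 75.5% where the truth is 70.0%. The overstatement needs no imbalance in deaths; the neutral look does.

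**The case against.** **A reader might infer that the plan censors deaths at death.** It does not say so. Cox and Kaplan-Meier can equally be run with deaths held as not recovered to Day 28; the ratio of about 0.8 above comes from a Cox model run that way. What decides the result is the unstated rule, not the two named methods. Detail is also deferred to a SAP outside the reviewed text, so the rule cannot be said to be missing from the whole plan. This stands. The finding is silence in the protocol section, together with a default that gives a misleading display.

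**A reader might infer that the trial could hide excess deaths.** The documents do not support that. Deaths would appear in adverse events to Day 60 (the primary endpoint), serious adverse event summaries, mortality to Day 60, the ordinal scale at Days 14 and 28, and the DMC's review of adverse event listings. The percentage recovered at Days 14 and 28 among all randomized patients would also reflect them, provided that deaths count as not recovered and are not imputed. In the main case, about 5 versus 1 deaths among 20 per arm (0.245 × 20 = 4.9; 0.071 × 20 = 1.4) would be seen. Any masking is confined to time to recovery.

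**The shift is small against the noise.** About 26 recoveries give a standard error of the log ratio near 2/√26 = 0.39. A ratio of 0.80 would have a 95% interval of about 0.37 to 1.7, and moving from 1.00 to 0.80 is just over half a standard error (0.22/0.39). Section 9.8.4 plans no inferential statistics. This lowers the severity, but it does not excuse the display: the overstatement is a bias in a descriptive curve, and descriptive output is what this trial will report.

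**A cause-specific ratio is a legitimate estimand.** It correctly describes the recovery rate among those still alive. Making a subdistribution ratio the main one is a choice of question. That is fair, and it is why both ratios should be shown with their handling of deaths stated.

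**Conclusion.** The point holds as a gap in specification. Section 9.8.4.1 leaves open how deaths before recovery enter the three time-to-recovery analyses. Under the usual default of censoring at death, Kaplan-Meier overstates recovery in both arms, and an arm with excess deaths can look neutral on these endpoints. Under the assumed main case the display shows 75% in both arms against a true 61% versus 71%, and the ratio is about 1.0 or about 0.8 depending on the rule. These sizes rest on assumed constant hazards, an equal recovery hazard in the two arms and a large imbalance in deaths; the milder case roughly halves the difference. The documents do not establish that deaths will be censored at death, or that harm would go unseen in the trial as a whole. The endpoint is secondary in a 40-patient exploratory study, so this should be fixed before database lock but does not undermine the design.

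**What to change.** In Section 9.8.4.1 and the SAP, for all three time-to-recovery endpoints:

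- State that a patient who dies unrecovered counts as not recovered through Day 28.
- Replace the Kaplan-Meier recovery display with Aalen-Johansen cumulative incidence of recovery and of death, by arm.
- Report the Cox ratio with deaths kept at risk to Day 28, give the cause-specific ratio alongside, and label how each handles deaths.
- In Section 9.7.3, exclude recovery status after death from multiple imputation.

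No new data are needed, because clinical status is already collected daily to Day 28 and mortality to Day 60. The cost is some added wording and slightly more analysis work. Reported recovery percentages will be lower than Kaplan-Meier with deaths censored at death would give; in the examples above the drop is about 4 to 14 points in the main case, depending on the arm's mortality.

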9.8.4.2. Supportive Analysis

To assess the consistency of the Primary Analysis results, supportive analysis will be conducted using the Intent to Treat (ITT) and Per Protocol (PP) populations. Statistical methodology for the supportive analyses will be the same as that of the primary analysis, with the exception of the analysis population used.

9.8.4.3. Safety Summaries

Adverse Events

Adverse events will be coded using the most recent version of Medical Dictionary for Regulatory Activities (MedDRA). Treatment Emergent AE's (TEAE) are defined as events with an onset on or after the first treatment. TEAEs will be summarized by treatment group, System Organ Class, and preferred term. The following TEAE summaries will be provided:

- Overall (i.e., regardless of severity or relationship to treatment);
- By intensity (mild, moderate, severe, life threatening or death);
- By causality (definitely, probably, possibly, remotely or unrelated);
- By impact on study treatment (dose increased, dose not changed, dose rate reduced, dose reduced, drug interrupted, drug withdrawn, not applicable, or unknown).

In addition, separate summaries of serious adverse events, and adverse events resulting in discontinuation of study treatment will be presented.

Clinical Laboratory Data

All laboratory values will be listed. Laboratory measurements will also be summarized and presented by treatment group and time point.

CONFIDENTIAL Page 52 of 66

ECG

All ECG values will be listed. ECG measurements will also be summarized and presented by treatment group and time point.

Vital Signs

All vital sign findings will be listed and/or summarized.

Physical Examination

All physical examination findings will be listed and/or summarized.

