- [9] Biochemistry (Comprehensive Metabolic Panel (CMP))
 - Hepatic function indicators: total bilirubin, alkaline phosphatase (ALP), aspartate aminotransferase (AST), alanine aminotransferase (ALT), total protein, albumin, lactate dehydrogenase (LDH)
 - Renal function indicators: BUN, Serum creatinine, creatinine clearance, or eGFR
 - Electrolytes: sodium, potassium, chloride, calcium and bicarbonate
 - Other: Creatine phosphokinase (CPK), C-reactive protein (CRP), serum ferritin, d-dimer
- [10] Prothrombin time (PT) and International Normalized Ratio (INR)
- [11] ONLY performed on women of childbearing potential.
- [12] Urine samples will be tested for color, appearance, specific gravity, pH, protein, glucose, occult blood, ketones, leukocyte esterase, nitrite, bilirubin, urobilinogen, and microscopic examination of urine sediment.
- [13] Positive standard RT-PCR assay or equivalent testing completed within 7 days prior to Day 1 is acceptable for eligibility evaluation at screening.
- [14] Chest radiograph or CT will be performed if clinically indicated by the treating physician
- [15] **Randomization:** Patient number and treatment arm allocation is performed on Day 1, prior to any Day 1 study assessments
- [16] Patient follow-up should continue after discharge via approaches available to the site staff (e.g., telehealth visits, COVID-19 outpatient clinic, telephone calls, texts, and emails to the patient and close contacts).
- [17] Follow-up visits may be performed via phone or telehealth, as appropriate

CONFIDENTIAL Page 16 of 66

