4. STUDY DESIGN

4.1. OVERALL DESIGN

This is a phase II multi-center, randomized, open-label, 2 arm parallel-group controlled interventional prospective study of CX-4945 in patients with severe COVID-19. Up to approximately 40 patients will be enrolled into this study. A screening evaluation will occur within 7 days prior to Day 1. All qualified patients will be randomized at Day 1 in a ratio of 1:1 to one of the following two treatment arms:

- Arm A: SOC*/ best supportive care** in combination with CX-4945 1000 mg BID PO or
- Arm B: SOC*/ best supportive care** alone
- * The standard of care (SOC) is not pre-specified, may vary among patients, and may include agents with anti-viral activity, such as remdesivir, among others. Investigator discretion is to be applied for any established SOC. Active concomitant treatment with other investigational antivirals or immunomodulators are not permitted
- ** Best supportive care is defined as intensive care therapy according to current guidelines, evidence, and best practice, including but not limited to lung protective ventilation, thrombosis prophylaxis, renal replacement therapy when indicated, and access to advanced therapies including extracorporeal membrane oxygenation.

The total duration of the treatment will be 14 days. Patients will be followed up at 28, 45 and 60 days from the start of the treatment. The total duration for each patient in the study (including the screening) will be up to 67 days. For details on randomization see Randomization in **Section 6.1.2.**

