5.1.1. Inclusion Criteria

Patients must meet all of the following inclusion criteria to be eligible for enrollment in the study:

- 1. Male or non-pregnant female adult ≥ 18 years of age
- 2. Diagnosed or confirmation of COVID-19 infection by standard RT-PCR assay or equivalent testing within 7 days prior to randomization (Day1).
- 3. Hospitalized patient with severe illness caused by SARS-CoV-2 (**Note:** Prior or current use of remdesivir or dexamethasone (SOC) are allowed under the investigator's discretion. Concomitant treatment with other investigational antiviral drugs or immunomodulators are not permitted from Day1 through Day 28)
 - Symptoms of severe systemic illness/infection with COVID-19:
 - At least 1 of the following: fever, cough, sore throat, malaise, headache, muscle pain, shortness of breath at rest or with exertion, confusion, or symptoms of severe lower respiratory infection including dyspnea at rest or respiratory distress

AND

- Clinical signs indicative of severe systemic illness/infection with COVID-19
 - At least 1 of the following: $RR \ge 30$, $HR \ge 125$, SaO2 < 93% on room air or requires $\ge 2L$ oxygen in order to normalize SaO2.
- 4. Patient (or legally authorized representative) provides written informed consent prior to initiation of any study procedures.
- 5. Adequate hematopoietic capacity, as defined by the following:
 - a. Hemoglobin \geq 9.0 g/dL and not transfusion dependent
 - b. Platelets $> 100,000/\text{mm}^3$
 - c. Absolute neutrophil count $\geq 1500 \text{ cells/mm}^3$

CONFIDENTIAL Page 27 of 66

- 6. Adequate hepatic function, as defined by the following:
 - a. AST and ALT ≤ 2.5 times upper limit of normal (ULN)
 - b. Total bilirubin $\leq 1.5 \text{ x ULN}$
 - c. Albumin $\geq 2.5 \text{ g/dL}$
- 7. Absence of any active or recurring clinically significant hepatic disease and adequate renal function, as defined by the following:
 - a. Renal: calculated creatinine clearance >45 mL/min for patients with abnormal, increased creatinine levels (Cockcroft-Gault formula).
- 8. Ability to take oral medication and be willing to adhere to drug administration and premedication requirements (see **Section 6.3**) throughout study duration.

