6. STUDY TREATMENT

6.1. STUDY TREATMENT ADMINISTRATION

6.1.1. Investigational Drug Product Description

For this study, the investigational product is CX-4945 that will be assigned to the subjects randomized to the treatment Arm A.

Refer to Investigator Brochure or summary of product characteristics.

All subjects enrolled in the study (Arm A and Arm B) may be treated with SOC/best supportive care as per the investigator's discretion and in accordance with the site standard clinical practice. The patients randomized to the treatment Arm A will receive SOC/best supportive care therapy in combination with CX-4945. The patients randomized to the control Arm B will receive SOC/best supportive care alone.

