8.3.1. Definitions of Adverse Event (AE)

An adverse event (AE) is defined as any unfavorable or unintended sign, symptom, or disease that occurs or is reported by the patient to have occurred, or a worsening of a pre-existing condition. An adverse event may or may not be related to the study treatment.

AEs will be elicited through direct questioning and subject reports. Any abnormality in physical examination findings or laboratory results that the investigator believes is clinically significant (CS) to the research subject and that occurred after initiation of the first study treatment will be reported as AEs. Abnormal findings that are NOT clinically significant should not be recorded as an AE.

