8.3.4. Reporting of Adverse Events

Report initiation for all AEs and SAEs will begin at the time of randomization and continue until the end of final study visit. All events will be followed to resolution or until the subject completes the study. A final assessment of outcome will be made at that time.

All AEs must be recorded in the subject's study records. AEs will be reported using customary medical terminology along with the following information: the onset and end dates, whether the event is considered to be a SAE (see Section 8.3.2), the impact the event had on study treatment (see Section 8.3.4.1), the Common Terminology Criteria for Adverse Events (CTCAE) grade (intensity) of the event (see Section 8.3.3.1), the causality of the event (see Section 8.3.3.2), whether treatment was given as a result of the event (see Section 8.3.4.2), and the outcome of the event. (see Section 8.3.4.3)

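### The main adverse-event tables start at a first treatment that is undated for Arm B, not at randomization, and Arm B events on Days 1–14 must be coded as a drug action or unknown

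*Combined protocol and SAP*

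**What the plan says.** Two sections start the clock at randomization. The primary endpoint in section 3 is "Adverse Events experienced by patients from randomization to Day 60", and section 8.3.4 agrees: "Report initiation for all AEs and SAEs will begin at the time of randomization".

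Two sections start it at treatment:

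- Section 9.8.4.3: "Treatment Emergent AE's (TEAE) are defined as events with an onset on or after the first treatment". The overall, intensity, causality and impact-on-treatment summaries all rest on this definition and are shown by treatment group.
- Section 8.3.1: laboratory and examination abnormalities judged clinically significant that "occurred after initiation of the first study treatment will be reported as AEs".

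For the control arm, section 6.1.1 says "The patients randomized to the control Arm B will receive SOC/best supportive care alone". Section 4.1 adds that "The standard of care (SOC) is not pre-specified, may vary among patients", and inclusion criterion 3 that "Prior or current use of remdesivir or dexamethasone (SOC) are allowed". On timing in Arm A, footnote 15 of the schedule says "treatment arm allocation is performed on Day 1, prior to any Day 1 study assessments". Section 8.1.2 then puts the Day 1 assessments before treatment.

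Section 8.3.4.1 lists eight codes for the effect of an event on study treatment and permits *not applicable* only once the subject has left the Treatment Phase. The schedule places all subjects in that phase from Day 1 to Day 14, while investigational product is given in Arm A only.

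**The concern.** Safety is the primary objective, and Arm B is the only concurrent reference for background COVID-19 events. With no inferential statistics planned (section 9.8.4), the descriptive by-arm tables are the primary result, so their start date and codes carry the comparison.

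As written, the main tables do not cover the endpoint's stated window. An Arm A event between allocation and the first capsule belongs to the primary endpoint but drops out of the treatment-emergent tables if first treatment means CX-4945. For Arm B the analyst must decide what first treatment is, and the two arms could end up with different starts. The impact table asks what was done to a study drug that Arm B patients do not receive.

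Two of the rules, in 8.3.1 and 8.3.4.1, are instructions to sites. They shape what is recorded, not only how it is tabulated.

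**Working it through.** No sample-size or error-rate figure is involved, so the check sets the rules side by side and counts the codes.

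**1. Start rules.** Sections 3 and 8.3.4 give randomization. Section 9.8.4.3 gives first treatment, and 8.3.1 gives first study treatment for laboratory and examination findings. Section 8.2.1.3 asks for new or worsened examination abnormalities to be recorded as adverse events, judged against baseline, without naming either start. Sites therefore face instructions that do not agree.

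**2. Arm A gap.** The Day 1 order is allocation, assessments, then treatment. If the oral antiemetic is given after allocation, section 6.3.1 puts an hour or more between it and the capsules. Both allocation and first dose fall on Day 1, so I assume a gap of 1 to 24 hours.

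- Window: 60 × 24 = 1,440 h
- Lower: 1 / 1,440 = 0.07%
- Upper: 24 / 1,440 = 1.7%

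These are shares of time, not of events. The one-hour minimum does not apply to a patient using the transdermal patch, which is applied about a day before Day 1. Even then the pre-treatment assessments lie between allocation and first dose.

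**3. Arm B start: four possible readings.**

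- *First standard of care ever, possibly before randomization.* Collection starts at randomization, so every collected event qualifies and the window equals the endpoint's.
- *First standard of care after randomization.* This is the nearest to the Safety Population wording in 9.7.1.3, but that sentence decides who is included, not when events start. The lag is undated, because section 6.1.1 only permits such care. It is likely short in hospitalized patients with severe illness.
- *Randomization.* No discrepancy.
- *Study drug only.* The nominal 40 / 2 = 20 Arm B patients would have no treatment-emergent events. Section 9.8.4.3 summarizes these events by treatment group, so this reading is untenable.

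Two readings are harmless, one loses a short unknown interval, and one cannot be intended. The plan does not choose among them.

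**4. Impact codes.** Of the eight, six describe an action on the drug (an increase, no change, a slower rate, a lower dose, an interruption, a withdrawal). The others are *not applicable* and *unknown*. For an Arm B event on Days 1–14, 8 − 1 = 7 codes remain: six drug actions plus *unknown*. None of them says that there was no study drug.

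**5. What can be repaired later.** Onset dates are recorded (8.3.4), so events already entered can be re-counted from randomization. A laboratory or examination finding that a site never entered as an adverse event because of 8.3.1 cannot be recovered that way. Its value is listed, but without the investigator's judgement. The Arm B column of the impact table can be suppressed, but the forced codes stay in the data.

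**The case against.** The strongest reply is that little follows in practice. Collection from randomization removes the worst consequence of an early Arm B start, the Arm A gap is short, and *unknown* is always available, so no Arm B event is forced into a drug action. All data are listed (section 9.7), laboratory values are summarized by arm, the serious-event summary is not expressly limited to treatment-emergent events, and the monitoring committee reviews adverse-event listings (section 9.9). Section 9 also sends detailed data conventions to a separate SAP, which may settle the anchor.

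Most of this stands, and it limits the size of the point. It does not remove it. Section 9.8.4.3 does not leave the start open for the SAP. It states a definition that differs from the endpoint. Sections 8.3.1 and 8.3.4.1 govern recording at the site, which a later analysis document cannot fully correct.

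A reader might infer that the summary of events leading to discontinuation has the same defect. The text does not support that. Section 9.2.1 refers to study medication, and Table 2 shows none in Arm B, so the Arm B entry is a structural zero and no rule forces a code there.

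**Conclusion.** The point holds as two stated rules that misfire: a start date that differs from the primary endpoint's and is undefined for Arm B, and a code restriction that leaves Arm B events on Days 1–14 without a meaningful entry. It should be corrected, but the effect on event counts is probably small. That judgement assumes first dosing within hours of allocation on Day 1, and standard of care under way at or soon after randomization in nearly all Arm B patients. The documents do not give the actual lags.

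Three stronger inferences are not supported. A reader might conclude that Arm B events will be missing from the tables altogether, which requires the reading ruled out above. A reader might put a percentage on lost or miscoded events, but the documents give no event rates, and a share of time is not an estimate of it. A reader might also take the silence of section 9.7.1.3 on as-randomized or as-treated tabulation as an error. That is a convention of the kind the plan defers to the SAP.

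**What to change.** - **Sections 9.8.4.3 and 8.3.1:** count events with onset or worsening on or after randomization, through Day 60, in both arms. Judge worsening against the last assessment before randomization. For ECG that is screening, the only one available before Day 14. Use the Day 1 pre-treatment value as the reference only where no earlier value exists, as for IL-6. Using Day 1 for everything would reopen the gap, because allocation precedes the Day 1 assessments.
- **Supportive summary:** keep an Arm A summary counted from the first CX-4945 dose.
- **Section 8.3.4.1:** allow *not applicable* for all Arm B events, and present the impact-on-study-treatment table for Arm A only.

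The cost is wording in three sections and one case-report-form code rule, with no change to sample size or patient care. A few Arm A events before the first capsule, including any from the antiemetic, will enter the main table. Comparison with the supportive summary shows them. Because screening can be up to 7 days before Day 1, a finding first seen on Day 1 may have arisen before randomization, so the investigator's onset date must decide whether it counts.
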